10. SUBJECT COMPLETION/WITHDRAWAL

10.1. Completion

A subject will be considered to have completed the study if he or she has completed 1 year of open-label treatment. Subjects who prematurely discontinue study treatment for any reason before completion of the 1-year open-label treatment phase will not be considered to have completed the study. Subjects who require a concomitant AED(s) after initiating treatment with study drug and continue in the study until Month 12 will also not be considered to have completed the study.

10.2. Withdrawal From the Study

A subject will be withdrawn from the study for any of the following reasons:

- Lost to follow-up
- Withdrawal of consent
- The investigator or sponsor believes (eg, that for safety or tolerability reasons such as an adverse event) it is in the best interest of the subject to discontinue treatment.
- Death
- Other reasons
- If a female subject becomes pregnant during the study, she must be discontinued from the study and the pregnancy followed to term, if applicable.

During the study, subjects will also be withdrawn if:

- Subject develops status epilepticus not controlled by a single rescue agent.
- At the discretion of the investigator, subject develops any new seizure types or any clinically relevant safety issue.
- Subject requires greater than a 10-day course of medications that may impact bone metabolism, including intravenous or oral steroids, furosemide, growth hormone, NSAIDs, antacids, or calcium/vitamin D supplements.
- Subject develops nephrocalcinosis (diagnosed in any way) or develops a significant clinical adverse event (eg, serious event, treatment-limiting event, or other consideration) diagnosed as being related to a new kidney stone. Ultrasound results that suggest an asymptomatic kidney stone will not necessarily serve as a reason for withdrawal from the study.
- The investigator believes the subject to be at significant risk of suicidal or violent behavior.

If a subject discontinues treatment before the end of the open-label treatment phase, the end-of-study assessments should be obtained.

If a subject is lost to follow-up, every reasonable effort must be made by the study site personnel to contact the subject and determine the reason for discontinuation/withdrawal. The measures taken to follow-up must be documented.

When a subject withdraws before completing the study, the reason for withdrawal is to be documented in the CRF and in the source document. Study drug assigned to the withdrawn subject may not be assigned to another subject. Subjects who withdraw will not be replaced.

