4.3. Prohibitions and Restrictions

Potential subjects must be willing and able to adhere to the following prohibitions and restrictions during the course of the study to be eligible for participation:

1. A girl of childbearing potential who is heterosexually active must remain on a highly effective method of birth control (see Section 4.1, Inclusion Criteria).
2. Subjects must refrain from using any of the prohibited medications, including:
 - Ocular medications, except lubricating eye drops or topical antibiotics

- Furosemide, hydrochlorothiazide, vigabatrin, vitamin B₆ therapy for epilepsy, monoamine oxidase (A or B) inhibitors
- Any other medication that is a potent carbonic anhydrase inhibitor (eg, acetazolamide, furosemide, zonisamide)
- Citrate treatment
- Medications that may affect bone metabolism if taken for more than a 10-day treatment course, including intravenous or oral steroids, growth hormone, NSAIDs, or antacids

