8. PRESTUDY AND CONCOMITANT THERAPY

Prestudy AEDs and other medications taken within 2 years prior to the study must be recorded at screening.

Concomitant therapies must be recorded throughout the study beginning with the start of the first dose of study drug. Concomitant therapies should also be recorded beyond 30 days after the last dose of study drug, but only in conjunction with new or worsening adverse events or serious adverse events that meet the criteria outlined in Section [12.3.2](#), Serious Adverse Events.

All therapies (prescription or over-the-counter medications, including vaccines, vitamins, herbal supplements; non-pharmacologic therapies such as electrical stimulation, acupuncture, special diets, exercise regimens) different from the study drug must be recorded in the CRF. Modification of an effective preexisting therapy should not be made for the explicit purpose of entering a subject into the study.

For subjects receiving an AED at baseline, this AED should be tapered down and discontinued during the titration period. Concomitant AEDs at baseline used for any purpose will be withdrawn in one-third decrements during the 6- to 8-week titration period.

Only AED monotherapy will be used for both treatment groups. In the event of insufficient seizure control or intolerability, it should be explored first if a dosage adjustment of the study drug might be useful before adding another AED. However, subjects will not be discontinued from the study if 1 or more concomitant AEDs are added after initiating treatment with study drug. Data will be collected prior to the use of the concomitant AED(s) for the primary analysis. Data subsequently collected while on the concomitant AED(s) will be analyzed in a secondary analysis for each safety outcome of interest.

Other prohibited concomitant medications include:

- Ocular medications, except lubricating eye drops or topical antibiotics
- Furosemide, hydrochlorothiazide, vigabatrin, vitamin B₆ therapy for epilepsy, monoamine oxidase (A or B) inhibitors, or felbamate
- Any other medication that is a potent carbonic anhydrase inhibitor (eg, acetazolamide, furosemide, zonisamide)
- Citrate treatment
- Medications that may affect bone metabolism taken for more than a 10-day treatment course, including intravenous or oral steroids, growth hormone, NSAIDs, antacids, calcium, vitamin D, or multivitamins

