Subjects will be allowed to take calcium, vitamin D, and multivitamins as concomitant therapy provided the dosages fall within the range of recommended daily allowances for the age of the subject. These agents will only be allowed as prophylaxis against a deficiency, and not as a treatment for a previously diagnosed deficiency.

The sponsor must be notified in advance (or as soon as possible thereafter) of any instances in which prohibited therapies are administered.

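### Protocol Section 8 permits prophylactic calcium and vitamin D without a time limit, but Section 10.2 withdraws a child who requires more than 10 days of them and makes no exception for that use

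*Protocol*

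**What the plan says.** Four places in the current protocol bear on this.

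- **Section 4.3** restricts "Medications that may affect bone metabolism if taken for more than a 10-day treatment course" and gives its examples as "including intravenous or oral steroids, growth hormone, NSAIDs, or antacids". Calcium, vitamin D and multivitamins are not among them.
- **Section 8, prohibited list**, uses the same 10-day limit, but its examples run "including intravenous or oral steroids, growth hormone, NSAIDs, antacids, calcium, vitamin D, or multivitamins".
- **Section 8, the paragraph after that list**, states "Subjects will be allowed to take calcium, vitamin D, and multivitamins as concomitant therapy", provided the dosage stays within the recommended daily allowance for age. It adds: "These agents will only be allowed as prophylaxis against a deficiency, and not as a treatment for a previously diagnosed deficiency". It sets no limit on duration.
- **Section 10.2** lists, among the grounds on which subjects will be withdrawn, "Subject requires greater than a 10-day course of medications that may impact bone metabolism". Its examples end with "furosemide, growth hormone, NSAIDs, antacids, or calcium/vitamin D supplements". It mentions neither dose nor prophylaxis, and it does not refer back to Section 8.

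Section 10.2 also asks for end-of-study assessments at early discontinuation and says that withdrawn subjects are not replaced. Section 9.3 places a DEXA scan at early withdrawal.

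SAP Table 8 (Section 3.1) assigns scans on Days 31 to 270 to Month 6 and scans from Day 271 onward to Month 12. SAP Section 5.5 counts as major deviations both staying in the study after meeting a withdrawal criterion and receiving a disallowed co-treatment. The one sensitivity analysis in SAP Section 7 that removes data after a co-treatment starts concerns added antiepileptic drugs only.

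**The concern.** Bone mineralization is part of the primary objective, and the protocol itself classes these products among agents that may affect bone metabolism. A site that works from Section 8 keeps a child on daily prophylactic vitamin D. A site that works from Section 10.2 withdraws the same child. The wording can therefore decide who stays in the study until the Month 12 scan, and whether a child who stays is reported as a major deviation. The analysis plan has no table or sensitivity analysis that would let a reader of the report see how often this arose.

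**Working it through.** No arithmetic settles this point, so I set the four texts side by side.

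| Place | Calcium, vitamin D named | Multivitamins named | Time limit | Dose or purpose condition | Consequence |
|---|---|---|---|---|---|
| 4.3 | No | No | 10 days | None | Must refrain |
| 8, prohibited list | Yes | Yes | 10 days | None | Prohibited |
| 8, next paragraph | Yes | Yes | None | Within daily allowance; prophylaxis only | Allowed |
| 10.2 | Yes | No | 10 days | None | Withdrawn |

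**Step 1: one child, two instructions.** Take a child on daily vitamin D within the allowance, as prophylaxis, throughout the year. The permission in Section 8 is met on every day. From the eleventh day the course is longer than 10 days, and Section 10.2 names the product with no exception. On its literal wording the child is due for withdrawal while complying with Section 8.

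**Step 2: multivitamins.** Section 8 treats multivitamins exactly as it treats calcium and vitamin D. Section 10.2 does not name them, so the protocol does not say whether a multivitamin containing vitamin D meets the withdrawal criterion.

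**Step 3: what happens to the BMD data.** A withdrawn child should have an end-of-study DEXA scan.

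- On Day 271 or later, that scan falls in the Month 12 window and the child has a Month 12 value.
- On Day 270 or earlier, it falls in the Month 6 window (or, up to Day 30, the baseline window) and there is no Month 12 value. If a Month 6 scan already exists, SAP Section 3.1 uses the one nearest Day 180. For example, with scans on Day 180 and at withdrawal on Day 230, the distances are 0 and 230 − 180 = 50 days. The Day 180 scan is analysed and the withdrawal scan is only listed.

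The loss is therefore confined to Month 12 BMD for withdrawals before Day 271. The baseline scan and any analysed Month 6 scan remain in the safety analysis set.

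**Step 4: deviation counts.** Suppose the child in Step 1 stays in. Under Section 10.2 taken literally, the first SAP category (criterion met, not withdrawn) applies. Under the Section 8 list read without the paragraph that follows it, the second category (disallowed co-treatment) applies. Under the Section 8 permission, neither applies. The documents do not say which reading governs.

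**Step 5: size.** The plan's own sample size reproduces: 100/(1 − 0.29) = 141 per arm, 282 in total. Neither document gives a rate of calcium, vitamin D or multivitamin use. SAP Section 1 records that enrollment was stopped early, so 282 is not a count of children exposed to the conflict.

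**The case against.** The best defence is that the texts can be harmonised. Within Section 8, the permission directly follows the prohibited list and reads naturally as its exception. In Section 10.2, the requirement that a subject needs a course of medication suggests treatment, and Section 8 draws the same line between prophylaxis and treatment. The first part stands: I would not call Section 8 contradictory in itself. The second part is a possible reading, but Section 10.2 does not state it, and a site applying the words as written would withdraw the child. The lists in Section 4.3 and elsewhere are given as examples, so an omission is not a contradiction by itself. It still leaves three different lists for one rule.

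A reader might go further in five ways that the documents do not support.

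- **That BMD data are simply lost.** An early-withdrawal scan is required, earlier scans stay in, and no SAP rule drops BMD data because of supplements.
- **That furosemide shows the same conflict.** A drug can be banned outright and still have a separate, higher threshold for withdrawal.
- **That a low vitamin D result at Month 6 exposes the contradiction.** Supplements for a diagnosed deficiency are treatment. Section 8 does not permit that use, its list prohibits it beyond 10 days, and Section 10.2 withdraws for it. The texts agree.
- **That precision is visibly damaged.** With SD 0.4 the half-width is 1.96 × 0.4 × √(2/n), which gives 0.111 at 100 completers per arm and 0.124 at 80. The fall to 80 would be invented, and 0.124 still rounds to the stated 0.12. The 29% dropout allowance is not restricted by cause.
- **That the treatment comparison is biased.** Differences in site reading alone do not establish this in a randomised study, and the documents show no difference between arms in supplement use.

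The SAP is also not silent. Section 5.6 lists and summarises non-antiepileptic co-medication by ATC level and preferred term, and Section 5.2 summarises reasons for discontinuation. Neither isolates long courses of bone-active products.

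**Conclusion.** The point holds in a limited form. Section 10.2, read literally, withdraws children whose supplement use Section 8 permits, and the product lists in Sections 4.3, 8 and 10.2 do not match. The consequences are a missing Month 12 BMD value, without replacement, for any such child withdrawn before Day 271, and major-deviation counts that depend on the site's reading. This rests on taking Section 10.2 at its word; if the sponsor intended only therapeutic courses, the defect is that the protocol does not say so. The number of children affected, and any effect on the BMD comparison, cannot be derived from the documents, and I give no figure for either.

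**What to change.** **Protocol.** Reconcile Section 4.3, both parts of Section 8 and Section 10.2. Use one product list, and state once how the daily-allowance permission, the 10-day limit and withdrawal relate to each other. Which clinical rule applies is for the sponsor. The cost is a wording change in four places. With enrollment stopped, it mainly serves the children still being followed and the consistent classification of deviations.

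**SAP Section 5.6.** Add a table, by arm, of calcium, vitamin D, multivitamin and other bone-active courses longer than 10 days. It uses concomitant-therapy data already collected, so the cost is one table.

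**SAP Section 7.4 (optional).** Add a BMD sensitivity analysis that excludes data after the start of such a course, parallel to the existing one for added antiepileptic drugs. The cost is one further run. It would use a smaller data set, and the exclusion may itself be related to bone findings, so it should be labelled as supportive only.

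**SAP Section 5.5.** State which reading of the reconciled rule determines the two deviation categories.

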11. STATISTICAL METHODS

Statistical analysis will be done by the sponsor or under the authority of the sponsor. A general description of the statistical methods to be used to analyze the study data is outlined below. Specific details will be provided in the Statistical Analysis Plan.

11.1. Subject Information

All subjects who are randomized will be included in the analysis population.

11.2. Sample Size Determination

A total of 282 randomized subjects, 141 in each treatment group, will be recruited to the study. The sample size takes into account a 1-year dropout rate of 29%, which is a conservative estimate based on the dropout rates observed in a previous monotherapy study in the 6- to 15-year-old age group, Study TOPMAT-EPMN-106, including a dropout rate of 22% in the study overall (both double-blind and open-label phases) and a dropout rate of 35% for the double-blind phase. The sample size was estimated in order to achieve a sufficient precision for the estimates of the treatment effect on the key endpoints. The precision of the confidence interval (CI) estimates for the key safety parameters are shown below:

- *Annual change in BMD (L1-L4) Z-score:* In the Bone Mineral Density in Childhood Study (BMDCS), mean annual change in BMD (L1-L4) Z-score in 6- to 15-year-old healthy subjects was, as expected, minimal (0.01-0.07).³⁵ The standard deviation (SD) varied from 0.3 to 0.48 across sex and age groups.³⁵ Assuming an SD of 0.4, with 100 completed subjects per group, the 95% CI for the treatment difference will have a precision of 0.12.
- *Annual change in height Z-score in the 2- to 9-year-old age group:* In the monotherapy epilepsy study TOPMAT-EPMN-106, the observed change from baseline in mean height Z-score at 1 year among the 2- to 9-year-old subjects treated with topiramate 400 mg/day was -0.18, with an SD of 0.28.⁴⁰ Assuming that 53% of the subjects will be recruited in the 2- to 9-year-old age group, ie, 53 completed subjects per treatment group, the 95% CI for the treatment difference will have a precision of 0.11.
- *Incidence of kidney stone formation:* In the studies TOPMAT-PEP-3001 and TOPMAT-PEP-1002 in infants (1 month to 2 years of age), a 7% incidence of kidney stones was observed during the 1-year topiramate adjunctive treatment period.^{11,38} A sample size of 100 completed subjects per treatment group will provide a 95% CI (Wilson score CI) for the

treatment difference with a width of 0.12, assuming that the incidence of kidney stone formation is 7% and near zero in the topiramate group and the levetiracetam group, respectively.

- *Change in weight Z-score in the 2- to 15-year-old age group:* In the monotherapy epilepsy study TOPMAT-EPMN-106, a -0.59 decrease from baseline in weight Z-score, with an SD of 0.43, was observed after 1 year of treatment with topiramate 400 mg/day. Assuming an SD of 0.43, a sample size of 100 completed subjects per treatment group will provide a 95% CI with a precision of 0.12.

11.3. Pharmacokinetic Analyses

Data will be listed for all subjects with available plasma concentrations per treatment group.

All concentrations below the lowest quantifiable concentration or missing data will be labeled as such in the concentration data presentation. Concentrations below the lowest quantifiable concentration will be treated as zero in the summary statistics. All subjects and samples excluded from the analysis will be clearly documented in the study report.

For each treatment group, descriptive statistics, including arithmetic mean, SD, coefficient of variation, geometric mean, median, minimum, and maximum will be calculated for the topiramate or levetiracetam plasma concentrations at each sampling time.

Topiramate and levetiracetam plasma concentrations will be provided as listings.

11.4. Safety Analyses

The key safety endpoints will include:

- Percentage of subjects with kidney stones
- Change from baseline in weight Z-score over time
- The following height analyses will be conducted for prepubertal subjects (2 to 9 years of age), subjects 10 to 15 years of age, and subjects 2 to 15 years of age:
 - Height at 1 year postbaseline
 - Height change from baseline over time
 - Height Z-score at 1 year postbaseline
 - Change from baseline in height Z-score over time
 - Height velocity at 1 year postbaseline
 - Height velocity Z-score at 1 year postbaseline
 - Percentage of outlier subjects with height Z-score decrease of >0.5 , >1.0 , and >2.0 over time
- The following BMD and BMC endpoints:

- BMD and BMC over time
 - BMD and BMC change from baseline over time
 - Z-score for BMD and BMC over time
 - Change from baseline in Z-score for BMD and BMC over time
 - Percent change from baseline in BMD and BMC over time
 - Percentage of outlier subjects with BMD Z-score decrease of >0.5 , >1.0 , and >2.0 over time
- Change from baseline in biochemical markers of bone mineralization including: serum levels of alkaline phosphatase, calcium, phosphorus, parathyroid hormone (intact), 25-hydroxy-vitamin D, 1,25-dihydroxy vitamin D, and IGF-1
 - Change from baseline in serum and urine laboratory tests, eg, bicarbonate, ammonia, renal function tests, and LFTs
 - Change from baseline in bone age

Z-scores for the DEXA scans will be calculated locally at baseline and at M12 to determine eligibility for the study and the Post-Study Follow-Up phase, and centrally for all statistical analyses. The Z-score calculation will take the DEXA machine and the subject's age, sex, height, and ethnicity into consideration. The reference databases for calculating the Z-scores are provided in the DEXA Manual for this study.

Longitudinal endpoints will be analyzed using a mixed-model repeated measures (MMRM) analysis. The MMRM model will include treatment group, age group, visit, treatment-by-visit interaction, baseline measure, and baseline-by-visit interaction. An unstructured covariance will be used. Other appropriate covariance structures will be explored as needed. Confidence intervals with 95% confidence for the estimated treatment differences will be provided at each time point as appropriate. For proportion endpoints, 95% confidence intervals will be provided for the treatment difference. Each of the endpoints will also be summarized by age group.

Seizure counts, cognitive, developmental level, and behavioral assessments will be summarized by treatment group and age group. The incidence of suicide-related thoughts and behaviors as determined by the C-SSRS will be summarized by treatment group and age group.

For the cognitive assessments, standardized change from baseline scores will be calculated by computing the change for each postdose assessment score from the baseline assessment score, relative to the expected within-subject standard deviations for each Cogstate task. For the tasks for which lower scores indicate improvement (eg, Detection Test and Identification Test), the score will be multiplied by (-1), so that negative standardized scores represent a decline in cognitive performance consistently across all tasks.

A meaningful decline in cognition has been defined as a standardized change of less than -1.65 from the baseline assessment. These calculations will indicate meaningful decline at the subject level. For each individual score assessment, standardized change scores that meet the definition of a meaningful decline will be identified using a binary flag, where 1 represents a meaningful decline from baseline and 0 otherwise.

Group-based summary data (frequency distribution of the binary flags) will also be presented by computing the proportion of subjects who meet the criteria for meaningful decline at each postdose assessment.

In addition to the above endpoints, other safety-related endpoints may be included in the analyses and summarized if deemed necessary.

Adverse Events

The verbatim terms used in the CRF by investigators to identify adverse events will be coded using the Medical Dictionary for Regulatory Activities (MedDRA). All reported adverse events with onset during the treatment phase (ie, treatment-emergent adverse events, and adverse events that have worsened since baseline) will be included in the analysis. For each adverse event, the percentage of subjects who experience at least 1 occurrence of the given event will be summarized by treatment group and by age group.

Summaries, listings, datasets, or subject narratives may be provided, as appropriate, for those subjects who die, who discontinue treatment due to an adverse event, or who experience a severe or a serious adverse event.

Adverse events of clinical interest for topiramate are: effects on liver function; metabolic acidosis; effects on growth and maturation; vision abnormalities; oligohidrosis with hyperthermia and rash; hyperammonemia and encephalopathy; kidney stones; cognitive disorders; and suicidality.

Adverse events of clinical interest for levetiracetam are as listed previously, notably somnolence, asthenia, and behavior disturbances (especially hostility and nervousness).

Subjects with adverse events of special interest may be counted or listed.

Clinical Laboratory Tests

Laboratory data will be summarized by type of laboratory test. Reference ranges and markedly abnormal results (specified in the Statistical Analysis Plan) will be used in the summary of laboratory data. Descriptive statistics will be calculated for each laboratory analyte at baseline and at each scheduled time point. Changes from baseline results will be presented in pre- versus

posttreatment cross-tabulations (with classes for below, within, and above normal ranges). A listing of subjects with any laboratory results outside the reference ranges will be provided. A listing of subjects with any markedly abnormal laboratory results will also be provided.

Vital Signs

Descriptive statistics of temperature, heart rate, respiratory rate, and blood pressure (systolic and diastolic) values and changes from baseline will be summarized at each scheduled time point. The percentage of subjects with values beyond clinically important limits (using age-appropriate ranges) will be summarized.

Physical Examination/Neurologic Examination

Descriptive statistics of changes from baseline will be summarized at each scheduled time point.

